Study Design: A feasibility randomised controlled trial of 50 parents allocated on a 1:1 basis into intervention or treatment as usual (TAU), with an embedded process evaluation. We will collect service use data for cost comparison in a parallel feasibility economic evaluation. This will be conducted by a series of questionnaires and interviews.

Randomisation

Randomization will take place after participants have consented to the study and have had their eligibility confirmed by the screening process. Participants will be randomized on a 1:1 basis to the two study arms (VIG+ treatment as usual vs treatment as usual). The randomisation will be performed by the study statistician at the Cardiff Centre for Trials research.

Data collection methods:

From study participants:

- Interviews: Parents will be interviewed to determine eligibility to be included in the study; in addition to a few questions matching the inclusion/exclusion criteria, parents will be administered the Vineland-3 (Sparrow et al., 2016) to determine their child's overall adaptive skills score. Parents who enter the study will be interviewed to measure their levels of service use (CA-SUS; Byford et al., 1999) at baseline (before randomisation) and 6 months after randomisation.

 For the process evaluation, approximately 10 parents (five from each group) and approximately eight clinical staff (including VIG clinicians and Service Managers) will be interviewed at the 6-month follow up (semi-structured interviews) to investigate their experience of the study (intervention and evaluation acceptability); perceived effectiveness of VIG and implementation issues (VIG group only); barriers and facilitators for engagement with VIG (VIG group only), and contextual service factors that affect VIG delivery (VIG group only). Interviews will take place over the telephone or an online video platform (Teams or Zoom). Interviews will last between 30 minutes to one hour.

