The Skills Development Scale (VIG-SDS) includes 11 items rated on a 0-6 scale. VIG-SDS indicates what score is expected from the VIG practitioner dependent on their level of expertise. These scores will be used to estimate fidelity. Scoring the VIG-SDS does not require any information about the parent.

Data Analysis:

Quantitative data will be analysed using descriptive statistics (frequencies, means, standard deviations). Qualitative data will be analysed guided by the MRC framework for process evaluation (Moore et al., 2015): the analysis will combine a bottom-up with a top-down approach to identify key themes emerging in the data across process evaluation domains of context, implementation and mechanisms of impact.

More detail on the proposed analysis to address the primary and secondary feasibility questions is provided here:

Recruitment: The study will note the number of referrals directly from clinicians, the number of people on mailing lists emailed study information, the number of interested parents undergoing screening, number ineligible, reasons for ineligibility, numbers who consent to be randomised, numbers and reasons for refusal to be randomised. The recruitment rate will be estimated from the number of parents found to be eligible for the trial amongst those undergoing formal screening and the number of those screened who are randomised. The criterion to be met is that at least 50% of eligible parents participate, i.e., N=50 from 100 eligible).

Study retention: the percentage of participants who at the 6m follow-up have at least one questionnaire measure completed among all participants who consented to participate in the study. The criterion to be met is that at least 70% of recruited participants are retained at 6m follow up. The percentage of participants who at 6 month follow up provided data on the DBC2 among those recruited (likely primary outcome in the final trial) will be estimated.

VIG completion: the number of recruited participants who received 3 VIG cycles among the recruited intervention group. The criterion to be met here is that at least 80% of participants receive 3 VIG cycles. VIG cycle completion is defined as one meeting to take a video and one meeting to go through the shared review.

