Progression to a final trial: A traffic light system will determine readiness for a definitive RCT. It is anticipated that of about 100 families consenting to the study, at least 50 families will be recruited. A hypothesis testing approach will be used to determine the feasibility of recruitment (Lewis et al., 2021): A green signal for recruitment rate is defined as recruiting more than 50% of eligible families, 35-50% amber; and <35% red. With 90% power and 5% one-sided alpha, 97 families will need to be approached. If recruitment is within the amber zone, but above the critical value of 42, then minor changes will be required to improve recruitment, if recruitment is <42 then major changes will be required.

Traffic light signals (Avery et al., 2017) for study retention and VIG completion: A green signal for study retention rate will be to retain >70% of participants at 6m follow-up (60-69% amber, <60% red). A green signal for VIG completion will be >80% completing 3 VIG cycles (65-79% amber; <65% red). These three primary feasibility outcomes will be the basis for determining whether progression to a full trial is possible.

A green signal for measure completeness will be 100% - 80% of useable data for DBC2 scores (likely primary outcome in full trial). Any measure with <70% useable data will be reconsidered.

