7.2 Sampling

7.2.1 Size of sample

As this is a feasibility RCT, no power calculation was used to estimate the target sample size. The recruitment rate of similar studies (Chakkalackal et al., 2017; Coulman et al., 2020) was examined to determine an appropriate recruitment rate for the current study. Subsequently we estimated the adequacy of the proposed recruitment target to address the study's research questions. It is anticipated that of about 100 families consenting to the study, at least 50 participants will be recruited to the study. A hypothesis testing approach will be used to determine the feasibility of recruitment (Lewis et al., 2021). This is one of the three primary research objectives: A green signal for recruitment rate is defined as recruiting 50% of eligible families, 35-50% amber; and <35% red. With 90% power and 5% one-sided alpha, 97 families will need to be approached. If recruitment is within the amber zone, but above the critical value of 42, then minor changes will be required to improve recruitment, if recruitment is <42 then major changes will be required.

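### The minor/major split within amber recruitment is a fixed count of 42, which matches the plan's own test only at a denominator of about 97, and the denominator is not fixed

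*Protocol*

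**What the plan says.** Section 5 (Progression to a final trial) defines the zones for recruitment as rates: "A green signal for recruitment rate is defined as recruiting more than 50% of eligible families", then "35-50% amber; and <35% red". It sizes the test as follows: "With 90% power and 5% one-sided alpha, 97 families will need to be approached". It then splits amber by a count: "If recruitment is within the amber zone, but above the critical value of 42, then minor changes will be required to improve recruitment", and "if recruitment is <42 then major changes will be required". Section 7.2.1 (Size of sample) repeats the calculation and the split.

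The denominator is described in three ways. The calculation speaks of families approached (97). The Recruitment paragraph of section 5 uses eligible parents: "The criterion to be met is that at least 50% of eligible parents participate, i.e., N=50 from 100 eligible". The progression text and section 7.2.1 expect about 100 consenting families. The size of the trial is fixed on the other side of the fraction: "A feasibility randomised controlled trial of 50 parents allocated on a 1:1 basis into intervention or treatment as usual (TAU".

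**The concern.** A critical count belongs to one sample size. Here the colours depend on a rate, the split inside amber depends on a count, and nothing says that the test is made on exactly 97 families or that 42 is rescaled for another number. Because the trial aims at 50 randomised, the number of families needed to reach 50 is the quantity most likely to vary. The label may then disagree with the hypothesis test on which the rule is said to rest. Recruitment is one of three outcomes on which progression depends, and this label says how much must change before a full trial.

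**Working it through.** **Inputs.** Null rate 0.35 (red/amber bound), alternative 0.50 (green bound), one-sided alpha 0.05, power 0.90, n = 97, cut 42: section 5 (Progression) and section 7.2.1. Anticipated denominator 100: section 5 (Recruitment). Target 50 randomised: section 5 (Study Design).

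**1. The plan's figures reproduce.**

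- Normal approximation: n = [(1.645·√(0.35·0.65) + 1.282·√(0.5·0.5)) / 0.15]² = 90.3.
- With continuity correction: (90.3/4)·[1 + √(1 + 2/(90.3·0.15))]² = 96.8, so 97.
- Critical count at 97: 97·0.35 + 1.645·√(97·0.35·0.65) + 0.5 = 33.95 + 7.73 + 0.5 = 42.18, so 42.

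Both numbers are right for their inputs.

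**2. Where above 42 is the exact cut.** Take the smallest r with P(X ≥ r | n, 0.35) ≤ 0.05. It is 42 at n = 94 to 96, 43 at 97 and 98, and 44 at 99 to 101. So above 42 (43 or more) is the exact 5% cut only at 97 and 98.

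**3. Other denominators.**

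| Denominator | Exact cut | P(count above 42), true rate 35% | 50 recruited: rate | One-sided p against 35% |
|---|---|---|---|---|
| 97 | 43 | 0.036 | 51.5% (green) | 0.0006 |
| 100 | 44 | 0.059 | 50.0% | 0.0015 |
| 110 | 48 | 0.211 | 45.5% | 0.015 |
| 115 | 50 | 0.327 | 43.5% | 0.037 |
| 120 | 52 | 0.458 | 41.7% | 0.077 |
| 130 | 56 | not shown | 38.5% | 0.230 |
| 140 | 59 | not shown | 35.7% | 0.461 |
| 142 | 60 | not shown | 35.2% | 0.511 |

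The third column stops at 120 because beyond that the count no longer divides amber: 42/121 = 34.7% is already red, so every amber result is above 42.

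**4. At the anticipated 100.** Counts of 44 to 50 pass both the count rule and the test. A count of 43 is labelled minor, but its exact p is 0.059. A count of 42 has no label (p = 0.088).

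**5. With 50 recruited.** Amber means a denominator from 100 (50.0%) to 142 (35.2%), and 50 is above 42 throughout, so the label is always minor. The exact test passes up to 116 (50/116 = 43.1%, p = 0.043) and fails from 117 (50/117 = 42.7%, p = 0.0502) to 142.

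**6. Small denominators.** 38/80 = 47.5% gives p = 0.014 against 35% (exact cut at 80: 36), but 38 is below 42, so the label is major. At 85 or fewer no amber count can exceed 42, since 43/85 = 50.6% is green.

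**7. The gap.** One branch needs a count above 42 and the other a count below it. At n = 97, treating 42 as a pass gives alpha 5.6%; treating it as a fail gives 3.6%.

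**The case against.** The strongest defence is that the rule was built for about 97 families and the plan expects about 100. At 100 the count and the exact test differ only at 43, apart from the unlabelled 42. With 50 recruited they agree at every denominator from 100 to 116. This stands, and it limits the size of the point.

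The larger disagreements need recruitment to depart from plan. Denominators of 117 to 142 assume that recruitment stops at 50, whereas the text expects at least 50. The 38/80 case is a trial that fell short of its target. The range 117 to 142 covers 26 of the 43 amber denominators, but that is not a probability, because the denominators are not equally likely. Whether 100 itself is amber is also unsettled: the Recruitment paragraph and section 7.2.1 let exactly 50% meet the criterion, while the progression text asks for more. Nothing here depends on that.

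A reader might infer that 97 or 42 is miscalculated, or that the test is faulty because neither reading of 42 gives exactly 5% alpha and 90% power at 97. The documents do not support this. Above 42 at n = 97 gives alpha 3.6% and power 88.9%, which is ordinary discreteness in a binomial test designed by a normal approximation.

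A reader might also infer that the progression decision as a whole is unsound. It is not: the colour is set by the rate, both labels call for changes, the raw recruitment numbers are recorded, and the Trial Steering Committee gives an independent view.

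It can be said that rescaling a cut-off is a matter for the analysis plan. But the protocol states the count as the rule, in two places, so a reader applying it as written would use 42 whatever the denominator.

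**Conclusion.** The point holds as an inconsistency between a rate-based zone and a count-based split. The fixed count reproduces the plan's one-sided 5% test of 35% only at 97 to 98 families. At the anticipated 100 the discrepancy is one count (alpha 5.9% for above 42, exact cut 44). It grows as the denominator moves away: an amber trial with 50 recruited is always labelled minor, although the test fails at rates below about 43%, and a small trial with a good amber rate is labelled major. Exactly 42 is unassigned. Only the minor/major label within amber is at risk, so this should be fixed but does not threaten the trial. The figures assume exact binomial tails, a null rate of 35%, and, for the 117 to 142 range, recruitment stopping at 50.

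**What to change.** In section 5 (Progression to a final trial) and section 7.2.1:

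- Name one denominator for the recruitment rate. Eligible parents fits both the Recruitment criterion and the zone definition. Bring the references to families approached and consenting into line with it. Without this step no rule on the observed denominator can operate.
- Replace the count with a rule at that denominator: within amber, minor changes if the one-sided exact binomial test of 35% gives p ≤ 0.05, otherwise major. Every count then has a label.
- Give counts as examples only: at least 43 of 97 (alpha 3.6%, power 88.9%) and at least 44 of 100 (alpha 3.9%, power 90.3%).

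A lighter, approximate alternative is to state the cut as a rate, 42/97 = 43.3%, and say on which side equality falls.

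The cost is about two sentences in each of the two places. No new data are needed, since numbers screened, ineligible and randomised are already recorded. The power quoted for 97 families becomes about 89%. The change should be made before the recruitment results are judged.

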Children with LD with challenging behaviour or mental health problems are referred to specialist child mental health services for treatment and support. Specialist mental health services are increasingly under strain (NHS Digital, 2020a), with therapy waiting time approaching 12 months; these issues have been exacerbated due to the pandemic. Remote family interventions could be an effective solution for both families and specialist mental health services (Aref-Adib & [name], 2021). The NHS long-term plan proposes digital interventions should be adopted to ease the pressure on specialist child mental health services. The Children's Commissioner (Children's Commissioner for England Office, 2021) highlights that, post-pandemic, remote interventions are even more crucial for achieving the NHS long-term plan. Where staff have had the experience of remote interventions (during the

pandemic), they are keen to adopt them as a regular service offer, because they could improve access, waiting times and non-attendance rates (Sheehan et al., 2021).

Why is this research important?

Challenging behaviours and mental health problems in children with LD can lead to family breakdown and children have to move to specialist residential schools or inpatient units. Seventy per cent of about 6,000 children in residential schools are there because of challenging behaviour (Lenehan & Gerachty, 2017). Such placements cost up to £500m a year (Lenehan & Gerachty, 2017). A placement in Assessment and Treatment Units (ATUs) is estimated at £5m over three years per child (Lenehan, 2017). There are 250 children in ATUs (NHS Digital, 2020b). Parents say 'there is a better way' to support these children and families.

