8.3 Safety Reporting

In the unlikely event that any Serious Adverse Events (SAEs) related to the intervention or research procedures should occur, the CI is responsible for ensuring that all staff involved in this study are familiar with the content of this section. Cis are responsible for notifying the Study Co-ordinator and CI. All SAEs must be reported immediately (and within 24 hours of knowledge of the event) to the sponsor by the study team. SAEs will be assessed at all follow-up time points, and intervention delivery staff will be trained to report these directly to the study team at any point during the study. Rates of SAEs by study arm will be reported to the TSC, and if required, to the REC. Additional information about the potential harm of the intervention will be collected through qualitative interviews with all stakeholders.

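### The 6-month retention signal pools both arms, so it can be green while one arm is below the protocol's own 60% red limit

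*Protocol*

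**What the plan says.** Section 5 describes the design as "A feasibility randomised controlled trial of 50 parents allocated on a 1:1 basis into intervention or treatment as usual (TAU". Under Data Analysis, a participant counts as retained at 6 months if they "have at least one questionnaire measure completed among all participants who consented to participate in the study", and "The criterion to be met is that at least 70% of recruited participants are retained at 6m follow up". Under Progression to a final trial the traffic light reads "A green signal for study retention rate will be to retain >70% of participants at 6m follow-up (60-69% amber, <60% red". None of these statements names an arm.

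VIG completion is defined within one arm: "the number of recruited participants who received 3 VIG cycles among the recruited intervention group". On recruitment, retention and VIG completion the protocol then says: "These three primary feasibility outcomes will be the basis for determining whether progression to a full trial is possible".

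Two secondary quantities sit alongside. Section 5 asks for the percentage of recruited participants with 6-month data on the DBC2 (the likely primary outcome of a full trial), and it sets a green signal for useable DBC2 data at 80% or more. Neither is split by arm. By-arm reporting is written in for safety (section 8.3: "Rates of SAEs by study arm will be reported to the TSC"), and satisfaction scores are compared between groups, but retention is not.

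**The concern.** One progression criterion concerns the VIG arm alone and none concerns the TAU arm alone. A pooled percentage lets good retention in one arm offset poor retention in the other. The arms differ in contact: section 4.3 gives VIG parents three to five cycles of two meetings over at most 12 weeks on top of usual support. Both arms come from services described in section 1 as "with therapy waiting time approaching 12 months". A difference in retention is therefore possible.

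Differential loss is one of the things a feasibility trial should reveal about a definitive VIG plus TAU versus TAU comparison with parent-completed outcomes. Section 4.2 says the study must decide whether to go ahead unmodified, with named modifications, or not at all. A pooled green would indicate that retention needs no modification even where one arm falls below the limit that the protocol itself calls red.

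**Working it through.** **The plan's own figures.** The retention limits are stated without a calculation, so there is nothing to reproduce for them. The only calculated progression figure, for recruitment, does reproduce. A one-sample normal approximation with continuity correction, 35% against 50%, one-sided 5% and 90% power, gives n = 96.8, i.e. 97. The critical value is 97 × 0.35 + 1.645 × √(97 × 0.35 × 0.65) = 41.7, i.e. 42. It does not bear on retention.

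**Inputs.**
- 50 randomised 1:1 (section 5, Study Design); an even split gives 25 per arm.
- Green above 70%, red below 60% (Progression to a final trial).
- Denominator: the 50 recruited. The definition speaks of consented participants and the criterion of recruited ones. About 100 families are expected to consent, and that denominator would cap retention near 50%, so the recruited 50 are used here.
- True retention by arm: not given in the protocol, so assumed over a range.

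**Step 1: which counts are possible.** Pooled green (>70%) means at least 36 of 50, because 35/50 is exactly 70%. An arm is below 60% at 14 of 25 or fewer, because 15/25 = 60%.

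| Lower arm | Other arm | Pooled | Gap (points) |
|---|---|---|---|
| 14/25 (56%) | 22/25 (88%) | 36/50 (72%) | 32 |
| 13/25 (52%) | 23/25 (92%) | 36/50 (72%) | 40 |
| 12/25 (48%) | 24/25 (96%) | 36/50 (72%) | 48 |
| 11/25 (44%) | 25/25 (100%) | 36/50 (72%) | 56 |
| 14/25 (56%) | 25/25 (100%) | 39/50 (78%) | 44 |

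The smallest gap that hides an arm below 60% is 32 points. The highest pooled rate that can do so is 78%.

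**Step 2: how often it would happen.** Let X and Y be independent binomial counts with 25 per arm and true rates p1 and p2. Summing P(X = x) × P(Y = y) over all pairs with x + y ≥ 36 gives the chance of a pooled green. Restricting the sum to pairs with x ≤ 14 or y ≤ 14 gives the chance of green with an arm below 60%.

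| Assumed true retention | Pooled green | Green with an arm below 60% |
|---|---|---|
| 95% / 50% | 61% | 40% |
| 90% / 55% | 61% | 24% |
| 85% / 60% | 61% | 11% |
| 80% / 65% | 60% | 3% |
| 80% / 80% | 94% | 0.2% |
| 75% / 75% | 75% | 0.4% |

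Under the Data Analysis wording (at least 70%, so 35 of 50 passes), the smallest hiding gap falls to 28 points (14/25 with 21/25). The first two masking probabilities rise to 53% and 35%.

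**Step 3: does the DBC2 signal catch it?** Anyone with DBC2 data at 6 months has completed at least one questionnaire and so counts as retained. With one arm below 60%, pooled DBC2 completeness is therefore at most 39/50 = 78%, short of the 80% green limit, provided it is counted over recruited participants. The completeness paragraph does not state its denominator.

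**Step 4: precision of an arm-level rate.** For 14/25 the exact 95% confidence interval is 35% to 76%, which spans red, amber and green.

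**The case against.** Pooled retention is a defensible feasibility criterion, and the retention passages contain no numerical error on this point. Much of the case against making more of it stands.

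- A reader might infer that the feasibility of keeping a TAU comparator goes untested. The documents do not support that. TAU parents are half of the retention denominator, about five are to be interviewed on their experience of the study, and satisfaction is compared between groups. What is missing is a separate progression criterion.
- A reader might also infer that TAU is the arm that will drop out. The protocol does not say so. The long waits in section 1 are general background, and both arms come from the same lists and receive TAU. Retention means completing a questionnaire for the research team, and vouchers and completion options are the same in both arms. VIG also adds a meeting burden, so the direction is open.
- The masking needs a large gap. At moderate differences its probability is small.
- The DBC2 signal would give partial warning, subject to its denominator. It is not one of the three outcomes on which progression rests.
- The steering committee gives an independent view on the progression outcomes, and an analysis plan may well tabulate retention by arm. Simply reporting by arm is therefore not a gap in the protocol. The decision rule, however, is fixed in the protocol, and it is pooled.

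**Conclusion.** The point holds as a limited weakness in a stated decision rule. A green retention signal is compatible with one arm, either one, at 44-56%, below the protocol's own red limit, and none of the three primary criteria would show it. How much this matters depends on the unknown difference between arms: material at true gaps of 35 to 45 points (24-40%), modest at 25 points (11% at 85%/60%), minor at 15 points (3% at 80%/65%), and negligible when the arms are alike. These figures assume an even 25/25 split, independent participants, the recruited 50 as denominator and the >70% wording. The arm-level rates are assumptions. This is an improvement to consider rather than an error that invalidates the progression plan.

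**What to change.** In section 5, Progression to a final trial, add after the retention traffic light: 'A green signal for retention also requires that neither arm is below 60%. If one arm is, the signal is amber, and the plan for the full trial must address retention in that arm.' State that this is a flag and not a test, since an arm-level rate on 25 parents is too imprecise to carry a firm decision.

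The cost is one sentence and two percentages from data already held. The downside is a needless amber in about 0.2% of trials when both arms truly retain 80%, and 0.4% when both retain 75%.

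### The progression zones disagree with the protocol's own criteria at the green/amber border: exactly 70% retention and exactly 80% VIG completion meet the criterion but receive no signal

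*Protocol*

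**What the plan says.** Protocol section 5, Data Analysis, sets each criterion as an inclusive minimum:

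- Recruitment: "The criterion to be met is that at least 50% of eligible parents participate, i.e., N=50 from 100 eligible".
- Retention: "The criterion to be met is that at least 70% of recruited participants are retained at 6m follow up".
- VIG completion: "The criterion to be met here is that at least 80% of participants receive 3 VIG cycles".

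Further down section 5, under Progression to a final trial, the same three outcomes get traffic-light zones, with green as a strict inequality:

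- Recruitment: "recruiting more than 50% of eligible families, 35-50% amber; and <35% red".
- Retention: "A green signal for study retention rate will be to retain >70% of participants at 6m follow-up (60-69% amber, <60% red".
- VIG completion: "A green signal for VIG completion will be >80% completing 3 VIG cycles (65-79% amber; <65% red".

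Section 7.2.1 repeats the recruitment zones with a different green limit: "recruiting 50% of eligible families, 35-50% amber; and <35% red".

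Both sections subdivide the recruitment amber zone at a critical value of 42. Minor changes apply above 42 and major changes below it. Section 5 makes the three signals the basis for deciding whether a full trial is possible.

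**The concern.** A progression rule should give every possible result exactly one signal, and a result that meets the stated criterion should not get a lower signal or none. Here the inclusive minima and the strict green limits differ at one point for each outcome. For retention and completion the amber zone also stops a whole percentage point short of that limit, so the boundary value belongs nowhere.

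Section 4.2 promises a decision by pre-specified criteria among three courses: proceed unmodified, proceed with modifications, or do not proceed. The steering committee is to give an independent view on the outcome. A committee shown 35/50 or 20/25 would find the criterion met in one place and no signal in the other. At 50/100 it would find the criterion met, an amber signal, and in section 7.2.1 a green one as well. It would then have to choose which text governs with the result in view.

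**Working it through.** **Inputs.** 50 parents randomised 1:1, so 25 per arm (section 5, Study Design). Criteria and zones are as quoted. The recruitment test has 90% power, one-sided 5% alpha, 97 families and a critical value of 42 (sections 5 and 7.2.1).

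**1. The plan's own figure.** For a one-sample test of 35% against 50%:

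- n = [(1.645·√(0.35·0.65) + 1.282·√(0.5·0.5)) / 0.15]² = 90.3.
- With continuity correction: (n/4)·[1 + √(1 + 2/(n·0.15))]² = 96.8, rounded up to 97.
- Critical count at 97: 97·0.35 + 1.645·√(97·0.35·0.65) = 41.7, rounded up to 42.

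The 97 and the 42 both reproduce and are not in dispute.

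**2. Zones applied as written.**

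| Outcome | Count | Rate | Stated criterion | Signal, section 5 |
|---|---|---|---|---|
| Retention | 34/50 | 68% | not met | amber |
| | 35/50 | 70% | met | none |
| | 36/50 | 72% | met | green |
| VIG completion | 19/25 | 76% | not met | amber |
| | 20/25 | 80% | met | none |
| | 21/25 | 84% | met | green |
| Recruitment | 49/100 | 49% | not met | amber |
| | 50/100 | 50% | met | amber (green and amber in 7.2.1) |
| | 51/100 | 51% | met | green |

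With denominators of 50 and 25, the counts 35 and 20 are the only ones without a signal. Each is also the smallest count that meets its criterion.

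**3. Rounding.** Some neighbouring denominators give values inside the gaps: 34/49 = 69.4%, 36/52 = 69.2%, 19/24 = 79.2%. Rounding to whole percent turns these into amber. It cannot help 35/50 and 20/25, which are exactly 70% and 80%.

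**4. The count of 42.** Minor changes apply above 42 and major changes below 42. A count of exactly 42 (42/97 = 43.3%, inside amber) is given neither.

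**5. Chance of landing on a boundary count.** Binomial probability C(n,k)·p^k·(1−p)^(n−k). The protocol states no expected retention or completion rate, so the true rate p is an assumption and a range is shown.

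| Count | True rate: probability |
|---|---|
| 35/50 | 65%: 9%; 70%: 12%; 75%: 9%; 80%: 3.0%; 85%: 0.3% |
| 20/25 | 75%: 16%; 80%: 20%; 85%: 16%; 90%: 6.5% |
| 50/100 | 50%: 8% |

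**6. After alignment.** With green at ≥50%, ≥70% and ≥80%, and amber running continuously up to those limits, every count has one signal. The counts 50/100, 35/50 and 20/25 become green; 49/100, 34/50 and 19/25 stay amber. The test limits remain 35% and 50%, so 97 and 42 do not change.

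**The case against.** The best defence is that the intended reading can largely be recovered. The Data Analysis text fixes inclusive minima in advance, and amber ends at 69% and 79%. Read together, these suggest that 70% and 80% are green and that only the strict inequality sign is out of line. That is a fair reading for retention and completion, and it lowers the severity. It does not settle recruitment, where section 5 puts 50% expressly in amber and section 7.2.1 puts it in both zones.

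The effect also depends on the denominators. At 51 or 54 for retention, or 26, 27 or 28 for completion, no count falls in a gap. The figure 35/50 further assumes that the denominator is the 50 recruited; the retention definition also mentions all who consented, which is a separate question. These points limit how often the problem would arise, but it remains at the planned sample size.

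Three stronger readings are tempting, and the document does not support them:

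- **That recruitment has a gap at 50/100.** It does not. The count has an amber signal that conflicts with the criterion, and a second label in section 7.2.1.
- **That 35/50 and 20/25 are the planned or most likely results.** They are minimum passing counts. If true retention were 85%, 35/50 would have a probability of 0.3%.
- **That there is about a 29% chance that retention or completion lands on an unassigned value.** The sum 1 − 0.878·0.804 = 0.294 requires both true rates to sit exactly on their thresholds and the two outcomes to be independent. Nothing in the protocol supports either, and those who complete VIG are part of the retention sample.

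**Conclusion.** The inconsistency is real and rests on the protocol's text alone. Exactly 70% retention and exactly 80% VIG completion meet the stated criteria and have no signal under any rounding. Exactly 50% recruitment has conflicting signals, and a recruitment count of exactly 42 has no assigned consequence.

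The size is modest: one count per outcome at denominators of 50, 25 and 100. The probability is at most about 12% for 35/50, 20% for 20/25 and 8% for 50/100, reached when the true rate equals the threshold and falling away from it.

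A reader might infer that the go/no-go decision is at risk. It is not: the three percentage conflicts sit on the green/amber border and none on amber/red, so they bear on whether modifications are needed. The unassigned 42 lies within amber and bears on whether the changes are minor or major.

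This should be fixed before results are seen; it does not undermine the design.

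**What to change.** Reword Progression to a final trial in section 5, and section 7.2.1, so that the zones are contiguous and match the minima in the Data Analysis text:

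| Outcome | Green | Amber | Red |
|---|---|---|---|
| Recruitment | ≥50% | ≥35% to <50% | <35% |
| Retention | ≥70% | ≥60% to <70% | <60% |
| VIG completion | ≥80% | ≥65% to <80% | <65% |

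Also assign a recruitment count of exactly 42 to one side of the minor/major-changes rule, in the same words in both sections.

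The cost is a wording change. The sample size, the 97 families, the critical value of 42, data collection and procedures all stay as they are.
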